Grade ≥ 3	
• Interrupt study treatment and consider more frequent monitoring of ALT, AST, and bilirubin.• Restart study treatment at a reduced dose after lab abnormalities have resolved to at least CTCAE Grade ≤ 1 or baseline.• Discontinue if lab abnormalities cannot be reversed despite interruption of study treatment.• Discontinue if drug-related ALT or AST $>3 \times$ ULN in combination with total bilirubin $>2 \times$ ULN without other reasonable explanation, consistent with drug-induced liver injury (DILI).

ALT, alanine aminotransferase; AST, aspartate aminotransferase; CTCAE v.5.0, Common Terminology Criteria for Adverse Events version 4

Elevations of aminotransferases when hepatic metastases are present may not require dose modifications if there are no progressive changes in the aminotransferases (less than a doubling) and if there are no progressive elevations in serum bilirubin concentration or coagulation factors.

The following condition requires discontinuation of cabozantinib:

Drug-related ALT or AST $>3 \times$ ULN in combination with total bilirubin $>2 \times$ ULN without other reasonable explanation, consistent with drug-induced liver injury (DILI).

Infections and Infestations: Infections are commonly observed in cancer subjects.

Predisposing risk factor include a decreased immune status (e.g., after myelosuppressive anticancer therapies, splenectomy), destructive growth of the underlying malignancy

including bone marrow infiltration with suppression of normal hematopoiesis, as well as the presence of IV devices.

Infections and abscesses should be treated with appropriate local care and systemic therapy. Cabozantinib should be interrupted until adequate healing has taken place.

Blood and Lymphatic System Disorders: Hematological toxicities (i.e., neutropenia and thrombocytopenia) and associated complications have been observed after administration of cabozantinib and may be managed with dose interruptions and/or dose reductions. Subjects with hematologic toxicities may require additional or more frequent laboratory tests according to institutional guidelines.

Dose reductions or dose interruptions for hematological toxicities are not mandated but can be applied as clinically indicated. Supportive care for thrombocytopenia or anemia, such as transfusions, may be managed according to institutional guidelines. The use of colony-stimulating growth factors should be considered. Febrile neutropenia or evidence of infection associated with neutropenia must be assessed immediately and treated appropriately and in a timely manner according to institutional guidelines.

Fatigue: Common causes of fatigue, such as anemia, deconditioning, emotional distress (depression and/or anxiety), poor nutrition, dehydration, sleep disturbance, and hypothyroidism should be ruled out and treated according to standard of care.

Pharmacological management should be considered after disease specific morbidities have been excluded when not prohibited.

Weight Loss: Anorexia and weight loss should be managed according to local standard of care including nutritional support. Pharmacologic therapy should be considered for appetite enhancement when not prohibited by a particular protocol.

Corrected QT Prolongation: The effect of orally administered cabozantinib 140 mg qd on QTc interval was evaluated in a placebo-controlled study in subjects with MTC. A mean increase in QTcF of 10-15 ms was observed after 4 weeks after initiating cabozantinib treatment. A concentration-QTc relationship could not be definitively established. Changes in cardiac wave form morphology or new rhythms were not observed. No cabozantinib-treated subjects in this study had a QTcF > 500 ms. Review of the larger safety database (~5000 subjects exposed to cabozantinib in clinical trials and in post-marketing experience) confirmed the absence of safety concerns associated with QT prolongation. There were no events of torsades de pointes reported.

Concomitant treatment with strong cytochrome P450 (CYP) 3A4 inhibitors, which may increase cabozantinib plasma concentrations, should be avoided.

If at any time on study there is an increase in QTcF to an absolute value > 500 ms, two additional ECGs must be performed with intervals not less than 3 min apart within 30 min after the initial ECG.

If the average QTcF from the three ECGs is > 500 ms, the following actions must be taken:

- Interrupt cabozantinib treatment.

- Hospitalize symptomatic subjects (e.g., with palpitations, dizziness, syncope, orthostatic hypotension, a significant ventricular arrhythmia on ECG) for a thorough cardiology evaluation and management.
- Consider cardiology consultation for asymptomatic subjects for evaluation and management.
- Check electrolytes, especially magnesium, potassium, and calcium; correct abnormalities as clinically indicated.
- Check concomitant medications for any medication that may have contributed to QT prolongation, and if possible, permanently discontinue these medications (<http://www.qtdrugs.org>).
- Repeat ECG triplicates hourly until the average QTcF is \leq 500 msec, or otherwise determined by consultation with a cardiologist or appropriate expert.

Subjects with QTc prolongation and symptoms must be monitored closely until the QTc elevation and symptoms have resolved. Cabozantinib treatment may be restarted at a reduced dose level if all of the following conditions are met:

- Symptoms are determined to be unrelated to the QT interval prolongation.
- The QTcF value $>$ 500 ms is not confirmed.
- Cabozantinib treatment has been interrupted through a minimum of 1 week following the return of the QTcF to \leq 500 ms.
- QT prolongation can be unequivocally associated with an event other than cabozantinib.
- Cardiac evaluation confirms that symptoms are the consequence of QT interval prolongation.
- Recurrence of QTcF prolongation after reinitiation of study treatment at a reduced dose.
- Administration and is treatable/has been resolved.

Following reinitiation of study treatment, ECGs must be repeated weekly for 2 weeks, then every 2 weeks for 1 month, then according to the protocol-defined time points.

All study treatment must be permanently discontinued if either of the following applies:

Electrolyte Disorders: Serum electrolyte disorders including hyponatremia, hypokalemia, hypomagnesemia, and hypophosphatemia have been reported during treatment with cabozantinib, and serum electrolyte levels should be monitored frequently while receiving cabozantinib. Clinically relevant electrolyte disorders should be managed according to the dose modification guidelines. Standard clinical practice guidelines should be used for management of electrolyte disorders and may include oral or intravenous replacement.

Endocrine Disorders: Treatment-emergent elevation of thyroid-stimulating hormone (TSH) has been observed with cabozantinib treatment. Currently available data are insufficient to determine the mechanism of thyroid function test alterations and its clinical relevance. Management of thyroid dysfunction (e.g., symptomatic hypothyroidism) should follow accepted clinical practice guidelines.

Angioedema: Angioedema should be managed according to standard practice. The subject should be observed until symptoms resolve, with particular attention to maintaining an open airway.

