- Therapeutic doses of LMWH or anticoagulation with direct factor Xa inhibitors rivaroxaban, edoxaban, or apixaban is allowed in subjects without known brain metastases who are on a stable dose of the anticoagulant for at least 1 week before the first dose of study treatment without clinically significant hemorrhagic complications from the anticoagulation regimen or the tumor.

5.3.11 _____ The subject has prothrombin time (PT)/INR or partial thromboplastin time (PTT) test $\geq 1.3 \times \text{ULN}$ within 14 days before the first dose of study treatment.

5.3.12 _____ The subject has uncontrolled, significant intercurrent or recent illness including, but not limited to, the following conditions:

- Cardiovascular disorders:
 - Ongoing congestive heart failure exacerbation or New York Heart Association Class 4, unstable angina pectoris, serious cardiac arrhythmias.
 - Uncontrolled hypertension defined as sustained blood pressure (BP) $> 150 \text{ mm Hg}$ systolic or $> 100 \text{ mm Hg}$ diastolic despite optimal antihypertensive treatment. Uncontrolled hypertension needs to be determined based on persistently high blood pressure readings over more than 24 hours and should NOT be based on the blood pressure readings from one clinic visit. Blood pressure readings done at home or by primary care providers are acceptable. If a blood pressure reading on the day of screening is high, but there are documented acceptable ($\leq 150 \text{ mm Hg}$ systolic and $\leq 100 \text{ mm Hg}$ diastolic) blood pressure readings prior to or after the screening visit (with or without the use of anti-hypertensive medications), patient will not be considered to have uncontrolled hypertension.
 - Stroke (including transient ischemic attack [TIA]), myocardial infarction (MI), or other ischemic event, or symptomatic thromboembolic event (e.g., deep venous thrombosis, pulmonary embolism) occurring less than or equal to 6 months before first dose of cabozantinib. [Note: Subjects with a diagnosis of deep vein thrombosis (DVT) or incidentally detected asymptomatic and sub-segmental pulmonary embolism (PE) on routine scans are allowed if on a stable dose of anti-coagulation for at least 1 week before first dose of study treatment]
 - Clinically significant hematuria, hematemesis, or hemoptysis of > 0.5 teaspoon (2.5 ml) of red blood, or other history of significant bleeding (e.g., pulmonary hemorrhage) within 12 weeks before first dose.

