Arterial thrombotic events (e.g., TIA, MI) have been observed in studies with cabozantinib. Subjects should be evaluated for pre-existing risk factors for arterial thrombotic events such as diabetes mellitus, hyperlipidemia, hypertension, coronary artery disease, history of tobacco use, and cardiac and/or thromboembolic events that occurred prior to initiation of study treatment. Further treatment with cabozantinib should be discontinued in subjects who develop an acute MI, cerebral infarction, or any other clinically significant arterial thromboembolic complication.

Hypertension: Table 7.5 provides treatment guidelines for hypertension deemed related to cabozantinib. Blood pressure should be monitored in a constant position visit to visit, either sitting or supine in a relaxed setting. Decisions to reduce or interrupt the dose of study treatment must be based on BP readings taken by a medical professional and must be confirmed with a second measurement at least 5 minutes following the first measurement.

All study treatment should be permanently discontinued in subjects with hypertensive emergency.

Table 7.5: Management of Hypertension Associated with Cabozantinib

Criteria for Dose Modifications	Treatment/Cabozantinib Dose Modification
Subjects NOT receiving optimized anti-hypertensive therapy	
> 150 mm Hg (systolic) ^a and < 160 mm Hg OR > 100 mm Hg (diastolic) and < 110 mm Hg	
 Optimize antihypertensive medications by adding new or additional antihypertensive medications and/or increase dose of existing medications. Reduce cabozantinib treatment by one dose level if optimal antihypertensive therapy (usually to include 3 agents) does not result in BP <150 mm Hg systolic or <100 mm Hg diastolic If subject is symptomatic interrupt cabozantinib treatment

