≥ 160 mm Hg (systolic) OR ≥ 110 mm Hg (diastolic)	
 Reduce cabozantinib by one dose level^b or interrupt cabozantinib treatment per investigator discretion Add new or additional anti-hypertensive medications and/or increase dose of existing medications and monitor subject closely for hypotension. If optimized antihypertensive therapy (usually to include 3 agents) does not result in BP < 150 mm Hg systolic or < 100 mm Hg diastolic, cabozantinib treatment should be interrupted Cabozantinib treatment should be dose interrupted if upper limits of systolic BP (≥ 160 mm Hg) are sustained and not adequately manageable or if systolic BP is > 180 mm Hg or diastolic BP > 110 mm Hg, or if subject is symptomatic Re-start cabozantinib treatment at the most tolerable dose and re-escalate only if BP falls to and is sustained at < 150 mm Hg systolic and < 100 mm Hg diastolic
Hypertensive emergency ^c	
 Decide to initiate or adjust antihypertensive. Permanently discontinue all study treatment

^a The investigator may approve treatment at a lower threshold than systolic BP >150 or diastolic BP >100 based on their clinical judgment and assessment of the individual subject.

^b Permitted dose levels are defined by individual protocols and PI discretion.

^c Hypertensive emergency is defined as uncontrolled elevated BP with clinical evidence of progressive or impending end-organ damage (e.g., myocardial infarction/ischemia, intracranial hemorrhage, cerebral ischemia, pulmonary edema, encephalopathy, kidney damage).

Stomatitis and Mucositis: Preventive measures may include a comprehensive oral examination to identify and treat any potential risk for complications before study treatment is initiated. Appropriate correction of local factors should be instituted as indicated, such as modification of ill-fitting dentures and appropriate care of gingivitis. During treatment with cabozantinib, good oral hygiene and standard local treatments such as non-traumatic and non-irritating cleansing, and oral rinses (e.g., with a weak solution of salt and baking soda) should be maintained. Lips should be kept moisturized with lip balm. The use of lipstick, lip-gloss, and Vaseline should be avoided.

Local treatment should be instituted at the earliest onset of symptoms. Obtain bacterial/viral culture if oral infection is suspected and treat infection as clinically indicated.

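### Table 7.5 tests blood-pressure control with 'or' where 'and' is needed, so persistent isolated systolic or diastolic elevation misses the stated cabozantinib dose step

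*Combined protocol and SAP*

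**What the plan says.** Table 7.5 in section 7.1.1 sets cabozantinib dosing for treatment-related hypertension. A patient enters the first row with systolic pressure above 150 "and < 160 mm Hg OR > 100 mm Hg (diastolic) and < 110 mm Hg". Antihypertensives are then optimized, and cabozantinib goes down one level if that "does not result in BP <150 mm Hg systolic or <100 mm Hg diastolic". Symptomatic patients are interrupted.

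The second row covers 160 or more systolic, or 110 or more diastolic. Its first step is to reduce by one level "or interrupt cabozantinib treatment per investigator discretion". Its control test follows: if optimized therapy "does not result in BP < 150 mm Hg systolic or < 100 mm Hg diastolic, cabozantinib treatment should be interrupted". A further bullet interrupts for sustained, unmanageable systolic pressure of 160 or more, or "if systolic BP is > 180 mm Hg or diastolic BP > 110 mm Hg, or if subject is symptomatic". After a hold, the site may "re-escalate only if BP falls to and is sustained at < 150 mm Hg systolic and < 100 mm Hg diastolic".

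Elsewhere, exclusion 5.3.12 reads: "Uncontrolled hypertension defined as sustained blood pressure (BP) $> 150 \text{ mm Hg}$ systolic or $> 100 \text{ mm Hg}$ diastolic", despite optimal treatment. It accepts a patient with a high screening reading if there are "documented acceptable ($\leq 150 \text{ mm Hg}$ systolic and $\leq 100 \text{ mm Hg}$ diastolic) blood pressure readings".

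**The concern.** The two control tests use 'or' inside a negative. To fail to reach A or B is to reach neither, so the dose step needs both components to stay high. Every comparable rule in the protocol points the other way. Row entry is by either component, uncontrolled hypertension at eligibility is either component above its limit, and both acceptable screening readings and re-escalation require both components within limits.

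At stake are patient safety and consistent dosing. Section 3.1.4 lists hypertension among the adverse events seen in at least 20% of cabozantinib-treated subjects, and reports Grade 3 hypertension in 7% of the urothelial study at 60 mg. Up to three centers may apply this table. If the literal test is followed, the decision for isolated elevation passes to general rules that turn on grade, tolerability or judgment. The alternative is the permanent stop of all study treatment that section 7.1.1 requires for persistent uncontrolled hypertension. The intermediate one-level reduction is what drops out.

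**Working it through.** No plan figure is in dispute; the check is one of logic. Let S be systolic and D diastolic pressure, in whole mm Hg, on optimized therapy.

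**Inputs**
- First-row range (Table 7.5): S 151–159 or D 101–109, with S < 160 and D < 110.
- Control as written in both tests: S < 150 or D < 100.
- Control in the re-escalation bullet: S < 150 and D < 100.
- Uncontrolled in 5.3.12: S > 150 or D > 100.

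**Failure tests**
- As written: NOT(S < 150 or D < 100) = S ≥ 150 and D ≥ 100.
- With 'and': NOT(S < 150 and D < 100) = S ≥ 150 or D ≥ 100.

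**Sample readings that persist on optimal therapy**

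| Reading | Within first-row range | Dose step as written | Dose step with 'and' | Uncontrolled by 5.3.12 |
|---|---|---|---|---|
| 158/88 | yes | no | yes | yes |
| 145/105 | yes | no | yes | yes |
| 158/104 | yes | yes | yes | yes |

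**All first-row readings** on an illustrative grid (S from 110, D from 60):
- Isolated systolic elevation, S 151–159 with D 60–99: 9 × 40 = 360 pairs.
- Isolated diastolic elevation, D 101–109 with S 110–149: 40 × 9 = 360 pairs.
- Both high, S 150–159 with D 100–109: 10 × 10 = 100 pairs, less 150/100 (outside the row) = 99.
- Total: 360 + 360 + 99 = 819.

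The written test triggers the reduction for 99 of 819 pairs, and for 0 of the 720 isolated ones. The 'and' test triggers for all 819. These counts depend on the grid and show only the logic; they are not patient frequencies.

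**Second row.** Cabozantinib is already reduced or held on entry, and single-component triggers remain. After those, the written test misses only asymptomatic patients whose pressure on optimized therapy settles at S 150–159 with D < 100, or D 100–110 with S < 150.

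**The case against.** The best reply is that the literal reading defeats itself. A patient who enters at 158/88 already has a diastolic below 100, so the test would be met before any drug was added and could never detect treatment failure. A sensible clinician will read it component by component: whoever entered on systolic must get below 150, and whoever entered on diastolic below 100. On that reading 158/88 and 145/105 both lead to a reduction. This is a fair account of what was meant. It does not change what the sentence says, and a dosing table should not need repair by its reader.

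The second reply is that the protocol leaves ample room to act:
- Section 7.1 permits reductions at the investigator's discretion and changes at any time. It also says interruption or reduction should be considered when supportive care fails.
- Table 7.3 covers intolerable Grade 2 events that cannot be adequately managed, and Grade 3 events.
- A footnote to Table 7.5 lets the investigator treat at lower thresholds.
- Section 7.1.1 stops all study treatment for persistent uncontrolled hypertension.

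All of this stands and limits the harm. None of it supplies the directed one-level reduction for persistent isolated elevation.

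A small boundary point also stands. The 'and' test treats 150/90 as not controlled, whereas 5.3.12 accepts 150. That follows from the table's own strict limits, which the re-escalation bullet shares.

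**Conclusion.** The concern holds as a wording defect in a safety rule. Followed exactly, Table 7.5 gives no one-level reduction to an asymptomatic first-row patient whose systolic pressure stays at 151–159 with diastolic below 100, or whose diastolic stays at 101–109 with systolic below 150. The effect in the second row is minor. The conclusion rests on the literal reading; sites that read the test as requiring both components at goal will already act correctly. The protocol gives no basis for estimating how many patients are affected, and none is offered. The response-rate analysis and the sample size do not depend on it. It should be corrected because the rule governs a known toxicity of the study drug and the remedy is nearly free.

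**What to change.** In the control-test bullet of each of the first two rows of Table 7.5, replace 'or' with 'and', so that control means systolic below 150 mm Hg AND diastolic below 100 mm Hg. This matches the table's re-escalation bullet and leaves no first-row reading without a dose step. No other change to the table is needed. The cost is one word in each of two bullets, made through the usual amendment route, and a memo to sites. It adds no visits, tests or patients.

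### Section 7.1.1 (QTcF): two permanent-stop conditions sit in the restart list, so no first restart can qualify and the stop sentence has nothing under it

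*Combined protocol and SAP*

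**What the plan says.** The rule starts when a single QTcF above 500 ms leads to two further ECGs and the mean of the three is also above 500 ms. Cabozantinib is then interrupted, symptomatic subjects are hospitalised, and triplicate ECGs are repeated hourly until the mean is 500 ms or less, unless a cardiologist or similar expert decides otherwise.

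The restart rule follows: "Cabozantinib treatment may be restarted at a reduced dose level if all of the following conditions are met". The bullets beneath it are, in order:

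1. "Symptoms are determined to be unrelated to the QT interval prolongation"
2. "The QTcF value $>$ 500 ms is not confirmed"
3. "Cabozantinib treatment has been interrupted through a minimum of 1 week following the return of the QTcF to" 500 ms or less
4. "QT prolongation can be unequivocally associated with an event other than cabozantinib"
5. "Cardiac evaluation confirms that symptoms are the consequence of QT interval prolongation"
6. "Recurrence of QTcF prolongation after reinitiation of study treatment at a reduced dose"
7. A fragment that opens with the capitalised word Administration and says that something is treatable or has resolved.

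Next comes an ECG schedule for the weeks after restarting. Then comes "All study treatment must be permanently discontinued if either of the following applies", and the text that follows directly is the paragraph on electrolyte disorders.

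**The concern.** The list is a strict conjunction, so one bullet that cannot be met blocks every restart. Bullets 5 and 6 read as grounds for stopping for good, and the sentence that needs two such grounds is empty.

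Two things are at stake. A subject whose QTcF rose above 500 ms for a reversible reason, such as an electrolyte disturbance since corrected, could not go back on cabozantinib under the printed text. And the stop sentence covers all study treatment, so it would end pembrolizumab too, yet it gives no QTcF-specific trigger. The protocol allows up to three sites, and each would have to reconstruct a cardiac safety rule for itself.

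**Working it through.** The protocol gives no figure to reproduce here. The check is whether all seven bullets can hold together for a subject facing a first restart.

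| Bullet | Can it hold at a first restart? | Reads as |
|---|---|---|
| 1. Symptoms not due to QT prolongation | Yes | Restart |
| 2. QTcF above 500 ms not confirmed | Yes, if it refers to the repeat triplicates | Restart |
| 3. At least 1 week off drug after QTcF returns to 500 ms or less | Yes | Restart |
| 4. Another unequivocal cause | Yes | First half of a restart condition |
| 5. Symptoms due to QT prolongation | Not together with bullet 1, and not in a subject without symptoms | Stop |
| 6. Recurrence after restarting | No, because there has been no restart | Stop |
| 7. Treatable or resolved | Only as the end of bullet 4 | Second half of a restart condition |

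*Restart.* Bullet 6 alone defeats every first restart, whatever the other bullets say. Bullets 1 and 5 exclude each other for any subject with symptoms, so the list would also fail such a subject later.

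*Stop.* The word *either* calls for two conditions and none is printed below it. Exactly two restart bullets describe reasons to stop. The ECG schedule that precedes the stop sentence is the monitoring that would detect the recurrence in bullet 6.

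*Count after repair.* Seven bullets, less two moved, leaves five. Joining 4 and 7 makes four. The result is four restart conditions (1, 2, 3 and 4+7) and two stop conditions (5 and 6).

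*Does another section fill the gap?* The list of permanent-stop events near the start of Section 7.1.1 does not name QTc prolongation. The note to Table 7.3 refers the reader to Section 7.1.1 both for specific conditions and for re-treatment after a dose hold. Section 6.9 makes the conditions in Section 7 mandatory reasons for withdrawal. The last two lead back to the faulty text. Generic rules do remain: the Grade 4 rule in Table 7.3, the 6-week limit on interruptions in Section 7.1, and withdrawal on the investigator's judgement in Section 6.9.

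*Reach.* Section 3.1.2 reports no QTcF above 500 ms on cabozantinib 140 mg in the medullary thyroid cancer study (209 evaluable). With 0 events in 209, the one-sided 95% upper bound is 1 − 0.05^(1/209) = 0.014. Over 39 enrolled subjects that is 39 × 0.014 = 0.55, or fewer than one subject. This assumes that the rate carries over to a different population, a 40 mg dose and a combination with pembrolizumab.

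**The case against.** The strongest objection is that the text was extracted from a PDF by a program, and two bullets separated from their heading is what faulty extraction could produce. That cannot be ruled out without the page. Three features favour an error in the source: the stop bullets lie between the two halves of a single condition, bullet 4 ends in a full stop, and the fragment begins with a capital. The interleaving is the most persuasive, since simple reordering would not readily produce it. The punctuation and the capital are modest evidence.

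A second objection is that little turns on it. This largely stands. The restart fault withholds re-exposure, a physician could work out the intended meaning, and about 5000 exposed patients and subjects showed no QT safety concern and no torsades de pointes. One qualification is that eligibility excludes only QTcF above 500 ms, the same value that triggers the rule. A subject may therefore enter just below it, and the mean increase reported at 140 mg was 10 to 15 ms.

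A reader might also infer that bullet 2 is a second, independent block, because the rule is reached only once a mean above 500 ms has been found. The documents do not support this. Hourly repeat triplicates are ordered just above the list, bullet 3 presupposes a return to 500 ms or less, and bullet 2 is workable if it refers to those repeats. It is ambiguous, not impossible.

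**Conclusion.** The point holds as a drafting fault in an operative safety rule: as printed, no first restart can qualify and the QTcF stop sentence has no content. It rests on the printed order being that of the source, for which confidence is medium until the page is checked.

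A reader might go further and infer that the protocol has no means of stopping treatment for QT prolongation, or that the trial's results are at risk. Neither follows. The two stop conditions are displaced by a few lines, not missing. Interruption, hospitalisation of symptomatic subjects and repeat ECGs are all intact, and the generic stopping rules still apply. Sample size and the response-rate analysis do not depend on this list.

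Severity is low. Few subjects, perhaps none, are likely to meet the rule, and the restart error is conservative. It is still worth correcting, because a mandatory rule that ends both drugs should be applied in the same way at every site.

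**What to change.** First compare the list with the PDF page. If the order is the same there:

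- Move bullets 5 (symptoms caused by QT prolongation) and 6 (recurrence after restarting at a reduced dose) to stand directly under the permanent-stop sentence.
- Join bullets 4 and 7 into one condition: the prolongation is unequivocally attributable to something other than giving cabozantinib, and that cause is treatable or has resolved.
- Optionally, have the sponsor clarify that bullet 2 refers to the repeat triplicate ECGs. This is a clarification only, since bullet 3 already implies it.

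The cost is one list correction in the next amendment, with no change to visits, sample size or analysis.
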